23.1.1 Authorship

Authorship of publications should be in accordance with the Uniform Requirements of the International Committee of Medical Journal Editors (ICMJE³⁷, sometimes referred to as the Vancouver Criteria).

The Investigator(s) offered authorship will be asked to comment and approve the publication.

23.1.2 Site-specific publication(s) by Investigator(s)

For a multi-centre clinical trial, analyses based on single-site data usually have significant statistical limitations and frequently do not provide meaningful information for healthcare professionals or Subjects, and therefore may not be supported by Novo Nordisk. It is a Novo Nordisk policy that such individual reports do not precede the primary manuscript and should always reference the primary manuscript of the trial.

Novo Nordisk reserves the right to prior review of such publications. Further to allow for the primary manuscript to be published as the first, Novo Nordisk asks for deferment of publication of individual site results until the primary manuscript is accepted for publication. As Novo Nordisk wants to live up to the industry publication policy, submission of a primary publication will take place no later than 18 months after trial completion.

23.2 Investigator access to data and review of results

As owner of the trial database, Novo Nordisk has the discretion to determine who will have access to the database

Individual Investigators will have their own research Subjects' data, and will be provided with the randomisation code after results are available.

Protocol Date: 04 February 2016 | Novo Nordisk

 Trial ID: NN1218-3854
 Version:
 4.0

 UTN: U1111-1118-2480
 Status:
 Final

 EudraCT no.: 2010-024054-11
 Page:
 143 of 149

24 Retention of clinical trial documentation

Subject's medical records must be kept for the maximum period permitted by the hospital, institution or private practice.

The Investigator must agree to archive the documentation (this includes both electronic and paper-based records) pertaining to the trial in an archive after completion or discontinuation of the trial if not otherwise notified. The Investigator should not destroy any documents without prior permission from Novo Nordisk. If the Investigator cannot archive the documents at the trial site, Novo Nordisk can refer the Investigator to an independent archive provider that has a system in place to allow only the Investigator to access the files.

The Investigator must be able to access his/her trial documents without involving Novo Nordisk in any way. Site-specific CRFs and other Subject data (in an electronic readable format or as paper copies or prints) will be provided to the Investigator before access is revoked to the systems and/or electronic devices supplied by Novo Nordisk. These data must be retained by the trial site. If the provided data (e.g. the CD-ROM) is not readable during the entire storage period, the Investigator can request a new copy. A copy of all data will be stored by Novo Nordisk.

Novo Nordisk will maintain Novo Nordisk documentation pertaining to the trial for as long as the product is on the market plus 20 years.

The files from the trial site/institution must be retained for 15 years after the completion of the trial, or longer if required by local regulations or Novo Nordisk. In any case trial files cannot be destroyed until the trial site/institution is notified by Novo Nordisk. The deletion process must ensure confidentiality of data and must be done in accordance with local regulatory requirements.

Protocol Date: 04 February 2016 Novo Nordisk

Trial ID: NN1218-3854 UTN: U1111-1118-2480 EudraCT no.: 2010-024054-11

 Date:
 04 February 2016

 Version:
 4.0

 Status:
 Final

 Page:
 144 of 149

25 Institutional Review Boards/Independent Ethics Committees and regulatory authorities

Institutional Review Boards/Independent Ethics Committees

Written approval or favourable opinion must be obtained from IRB/IEC prior to commencement of the trial.

During the trial, the Investigator or Novo Nordisk, as applicable, must promptly report the following to the IRB/IEC, in accordance with local requirements: updates to IB, unexpected SAEs where a causal relationship cannot be ruled out, protocol amendments according to local requirements, deviations to the protocol implemented to eliminate immediate hazards to the Subjects, new information that may affect adversely the safety of the Subjects or the conduct of the trial (including new benefit-risk analysis in case it will have an impact on the planned follow-up of the Subjects), annually written summaries of the trial status, and other documents as required by the local IRB/IEC.

The Investigator must ensure submission of the CTR synopsis to the IRB/IEC.

Protocol amendments must not be implemented before approval or favourable opinion according to local regulations, unless necessary to eliminate immediate hazards to the Subjects.

The Investigator must maintain an accurate and complete record of all submissions made to the IRB/IEC. The records must be filed in the Investigator trial master file and copies must be sent to Novo Nordisk.

Regulatory Authorities

Regulatory authorities will receive the clinical trial application, protocol amendments, reports on SAEs, and the CTR according to national requirements.

04 February 2016 | Novo Nordisk Protocol Date:

4.0

Trial ID: NN1218-3854 Version: UTN: U1111-1118-2480 Status: EudraCT no.: 2010-024054-11

Final Page: 145 of 149

26 Indemnity statement

Novo Nordisk carries product liability for its products, and liability as assumed under the special laws, acts and/or guidelines for conducting clinical trials in any country, unless others have shown negligence.

Novo Nordisk assumes no liability in the event of negligence, or any other liability of the sites or Investigators conducting the trial, or by persons for whom the said site or Investigator are responsible.

Novo Nordisk accepts liability in accordance with:

Further, this protocol amendment specifies how the technical complaints for this device for investigational use will be collected in Russia.

In this protocol amendment:

- Any new text is written *in italics*.
- Any text deleted from the protocol is written using strike through.

2 Changes

1

Section 8.3.2.2 Self-measured plasma glucose

At the start of the run-in visit (Visit 2), the Subject will be provided with a BG meter, including lancets, the corresponding lancing device and plasma calibrated test stripes for BG meters. The Subject will be instructed verbally on how to use the device according to the manufacturer's instructions. The Subject will also be provided with written instructions in local language. Sites will, as necessary, go through the instructions of use with the Subject during visits to the site. It is the site's responsibility to ensure that the subject is familiar with the use of the device, as the device's display will be in English.

The BG meter used in this trial will be the Ascensia Contour[®] Next Link blood glucose monitoring system (Ascensia Diabetes Care, Basal, CH). The Ascensia Contour[®] Next Link blood glucose monitoring system is CE marked in the European Union, but is not marketed, licensed or approved in Russia. Accordingly, the device will be marked as "for investigational use only" in Russia.

Novo Nordisk A/S will be responsible for ensuring subjects' safety when using this device for investigational use during this trial.

All technical complaints, AEs and SAEs related to the BG meters must be reported to Novo Nordisk. using a separate Technical Complaint Form for BG meters and on the AE Form and SIF according to the process and reporting timelines specified in Section 12. The Investigator must inform the local Ethics Committees of such events according to local legislation.

Section 8.3.2.6 Back-up kit

Protocol Amendment	CONFIDENTIAL	Date:	15 September 2016	Novo Nordisk
Trial ID: NN1218-3854		Version:	1.0	
UTN: U1111-1118-2480		Status:	Final	
EudraCT No.: 2010-024054-11		Page:	4 of 5	

Glucagon for injection (reimbursed by Novo Nordisk affiliate, or supplied by the *Novo Nordisk affiliate*-central lab in Russia)

Section 9.5.1 Auxiliaries supplied by Novo Nordisk

• Bayer Ascensia Contour® Next Link meters blood glucose monitoring system (CE-approved marked in EU) marked as "for investigational use only", and strips, lancets and control solution for BG meters

9.5.2 Auxiliaries supplied by site

• Glucagon for injection (reimbursed by Novo Nordisk affiliate, supplied by the *Novo Nordisk* affiliate -central lab in Russia)

12.1.5 Technical complaint

A technical complaint is any written, electronic, or oral communication that alleges product (medicine or device for investigational use in Russia) defects. The technical complaint may be associated with an AE, but does not concern the AE itself.

Examples of technical complaints:

- The physical or chemical appearance of trial products in the vials (e.g. discoloration, particles or contamination)
- The 10 mL vial packaging material (e.g. leakage, cracks, rubber membrane issues or errors in labelling text)
- Any technical malfunction of the BG meter

12.4.1 Reporting of technical complaints

All technical complaints on any of the following trial products and devices for investigational use:

- Faster-acting insulin aspart, 100 U/mL, 10 mL vial
- Insulin aspart (NovoRapid®), 100 U/mL, 10 mL vial
- Ascensia Contour[®] Next Link blood glucose monitoring system (BG meter)

Technical complaints must be reported on a separate Technical Complaint Form in the eCRF for each Novo Nordisk product listed. If the technical complaint involves more than one batch/code

Protocol Amendment		Date:	15 September 2016	Novo Nordisk
Trial ID: NN1218-3854	CONFIDENTIAL	Version:	1.0	
UTN: U1111-1118-2480		Status:	Final	

Page:

5 of 5

number or more than one DUN, a Technical Complaint Form for each batch/code number or for each DUN must be completed in the eCRF.

Technical complaints concerning the BG meters must be reported using the paper based Technical Complaint Form for BG meters.

1.1 Trial information

This is a double-blind, randomised, multicentre, multinational, active controlled, treat-to-target, parallel group trial with a 4-week run-in and a 16-week treatment period comparing the effect and safety of continuous subcutaneous insulin infusion (CSII) of fast-acting insulin aspart versus NovoRapid® in adult subjects with type 1 diabetes mellitus (T1DM). Subjects entering the trial will stay on their own insulin pump.

The total duration of the trial is approximately 26 weeks split into the following periods (see [Figure 1-1](#)):

- ≤ 2-week for screening period
- A 4-week run-in period primarily for reinforcement of subject training in trial procedures, diabetes education and collecting baseline assessments
- A 16-week double-blinded treatment period
- A 7-day and 30-day follow-up period

Note: Prior to randomisation and after end of treatment subjects are on marketed product.

Baseline is defined as randomisation.

Figure 1-1 Trial design

Up to 50% of the eligible subjects will be allowed to wear their own real-time continuous glucose monitoring (CGM) device during the entire course of the trial. The remaining enrolled Subjects will not be allowed to wear a CGM device except for three pre-specified periods. During these periods a

blinded CGM device will be handed out to all subjects by the Investigator, including subjects wearing their own CGM. Randomisation is stratified according to the use of own real-time CGM.

The primary objective is to confirm the effect of continuous subcutaneous insulin infusion (CSII) treatment with fast-acting insulin aspart in terms of glycaemic control by comparing it to CSII treatment with NovoRapid[®], in adults with Type 1 Diabetes Mellitus (T1DM), using a non-inferiority approach.

The secondary objectives are to confirm superiority of CSII treatment with fast-acting insulin aspart compared to CSII treatment with NovoRapid[®] in adults with T1DM, in terms of:

- Postprandial glucose regulation (meal test)
- Overall glycaemic control (HbA_{1c})
- Postprandial glucose excursions (1,5-anhydroglucitol)
- Time spent in low interstitial glucose (CGM)

To compare the effect and safety of CSII treatment with fast-acting insulin aspart vs. CSII treatment with NovoRapid[®] in adults with T1DM.

For further details see the trial protocol.

1.2 Scope of the statistical analysis plan

This statistical analysis plan (SAP) is based on the statistical considerations of NN1218-3854 as planned in the trial protocol *Efficacy and Safety of Continuous Subcutaneous Insulin Infusion of Faster-acting Insulin Aspart compared to NovoRapid[®] in Adults with Type 1 Diabetes*, version 4.0 (dated 04 February 2016). It contains a more detailed description for deriving and calculation of endpoints. Furthermore, it details changes to the statistical considerations presented in the protocol.

The changes to the statistical considerations proposed in this SAP and the reasons for the changes will be reported in the clinical trial report (CTR).

2 Statistical considerations

General considerations

In general, for endpoints evaluated as a change from baseline and/or where a baseline adjustment is made, baseline is defined as information collected at randomisation (Visit 6). In case a measurement is not available at randomisation, the most recent measurement prior to randomisation will be used as baseline.

Two observation periods are defined, “in-trial” and “on-treatment”, and it will be specified which period each analysis will use.

- **In-trial:** the observation period from date of randomisation and until last trial -related Subject-site contact. The in-trial observation period includes data collected after discontinuation of randomised treatment.
- **On-treatment:** the observation period from date of first dose of randomised NovoRapid[®]/fast-acting insulin aspart and no later than 7 days after the day of last dose of randomised NovoRapid[®]/fast-acting insulin aspart. The on-treatment observation period includes data collected up to and including 7 days after discontinuation of randomised treatment.

All efficacy endpoints will be summarised and analysed using the full analysis set (FAS), unless otherwise stated. Safety endpoints will be summarised using the safety analysis set and analysed using the FAS.

Presentation of results from a statistical analysis will include the estimated mean treatment effects (LSMeans) for change from baseline, if applicable. Estimated mean treatment differences (or ratios) will be presented together with two-sided 95% confidence interval (CI) for all endpoints analysed statistically.

For endpoints measured over time, mean values will be plotted to explore the trajectory over time. For survival endpoints (e.g. drop-out pattern) Kaplan-Meier plots are presented for each treatment.

Data collected before randomisation (Visit 6) will only be summarised descriptively.

Subjects that prematurely discontinue from treatment or withdraw from trial will attend end of treatment visits called visit 22A and 22B. Data collected at these visits will be reallocated to the next scheduled visit where the given assessment is planned. As a general rule, all observed values from randomised subjects will be used in all statistical analyses, but in case two different values are associated to the same visit in time, the use of a given value will depend on the estimand of interest. For the primary estimand the reallocated on-treatment value will not be used and for the secondary estimand the reallocated on-treatment value will be used. The estimands will be defined in the next section.

Testing strategy and estimands

The primary objective, to confirm the effect of CSII treatment with fast-acting insulin aspart in terms of glycaemic control by comparing it to CSII treatment with NovoRapid[®], in adults with T1DM, will be assessed by the change from baseline in HbA_{1c} using a non-inferiority approach.

More specifically the upper limit of the 95% confidence interval for the difference between fast-acting insulin aspart and NovoRapid[®] should be compared to a non-inferiority margin of 0.4%. If it is below or equal to 0.4% non-inferiority will be considered established and effect demonstrated.

The trial also aims to compare CSII treatment with fast-acting insulin aspart to NovoRapid[®] for a number of confirmatory secondary endpoints. The family-wise type I error rate will be controlled in the strong sense using a hierarchical (fixed sequence) testing procedure for the primary estimand. This is based on a priority ordering of the null-hypotheses, and testing them in this order using the two-sided 95% confidence interval approach until an insignificant result appears. The effect is that rejection of a null hypothesis only will be considered for analyses where all previous null-hypotheses have been rejected in favour of fast-acting insulin aspart.

The steps in the hierarchical testing procedure are as follows:

Step 1 (Primary analysis): HbA_{1c} non-inferiority of fast-acting insulin aspart versus NovoRapid[®]

Step 2: 1-hour postprandial glucose (PPG) increment (meal test) superiority of fast-acting insulin aspart versus NovoRapid[®]

Step 3: HbA_{1c} superiority of fast-acting insulin aspart versus NovoRapid[®]

Step 4: 1,5-Anhydroglucitol superiority of fast-acting insulin aspart versus NovoRapid[®]

Step 5: time spent in low interstitial glucose (IG) (≤ 3.9 mmol/L [70 mg/dL]) superiority of fast-acting insulin aspart versus NovoRapid[®]

Primary estimand (de facto)

The primary estimand is defined as the treatment difference between Subjects randomised to CSII treatment with fast-acting insulin aspart and CSII treatment with NovoRapid[®] in adults with T1DM assessed by change from baseline in HbA_{1c} 16 weeks after randomisation for all randomised Subjects regardless of treatment discontinuation or use of ancillary therapies. This estimand is a de facto estimand addressing effectiveness.

The primary estimand assesses the expected benefit that a Subject can achieve if prescribed to CSII treatment with fast-acting insulin aspart as compared to CSII treatment with NovoRapid[®] in adults with T1DM. By not putting any restrictions on the randomised treatment adherence, this estimand aims at a difference as close as possible to the one that can be expected in real-world clinical practice, provided that the treatment adherence and use of ancillary therapies reflects clinical practice. Thereby the primary estimand provides a clinically relevant treatment difference for clinicians concerning the glycaemic effect of CSII treatment with fast-acting insulin aspart as compared to CSII treatment with NovoRapid[®] in the day to day life in adults with T1DM.

Secondary estimand (de jure)

Unlike the primary estimand, the secondary estimand is defined as the treatment difference in change from baseline in HbA_{1c} 16 weeks after randomisation between CSII treatment with fast-

acting insulin aspart and CSII treatment with NovoRapid[®] in adult Subjects with T1DM if Subjects continue on-treatment until 16 weeks. This estimand is a de jure estimand, addressing efficacy.

As an alternative to the primary estimand, this estimand provides a more hypothetical treatment difference, but may also be the most sensitive for a non-inferiority comparison, since the marketed product that Subjects discontinuing from randomised treatment are switched to may equalize the treatment effect.

The two estimands will be repeated for the endpoints:

- 1-hour PPG increment (meal test)
- 1,5-Anhydroglucitol
- time spent in low IG (≤ 3.9 mmol/L [70 mg/dL]) (CGM)

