8.1.8 Withdrawal procedures

8.1.8.1 Premature discontinuation of trial product

If a Subject is discontinued from trial product, as described in Section 6.6.1 after randomisation (Visit 6), the Investigator must ensure that every possible effort is made to undertake the following procedures:

 Trial ID: NN1218-3854
 Version:
 4.0

 UTN: U1111-1118-2480
 Status:
 Final

 EudraCT no.: 2010-024054-11
 Page:
 44 of 149

Subjects discontinuing before or at Visit 12 (Week 6)

- The Subject needs to be called in for a 22A including CGM fitting as soon as possible after awareness of the trial product discontinuation intention. The meal test at Visit 22A should be performed while the Subject still is on trial product according to randomisation unless this is not feasible for safety reasons as judged by the Investigator. (Confirmation that the meal test was performed on trial product will be recorded in the eCRF).
- The Subject will be asked to remain on trial product until completion of Visit 22B (Confirmation that the Subject was on trial product will be recorded in the eCRF)
- The Visit 22B needs to be scheduled 7 days after Visit 22A and serves mainly for transfer of CGM data as specified in Section 2. No additional CGM fitting is needed for these Subjects at this visit.
- The CGM assessment on visit 14 can be omitted for these Subjects

At Visit 22B a treatment discontinuation session must be made in IV/WRS and reason for discontinuation of trial product must be specified in the End of Treatment/Trial form in the eCRF. Final drug accountability must be performed even if the Subject is not able to come to the trial site.

At Visit 22B the Subject should be switched to a suitable marketed product at the discretion of the Investigator. The medication should be recorded on the diabetes treatment history form (please see 8.2.5) in the eCRF.

If the Subject does not wish to continue on trial product until visit 22B (or if continuation on trial product is not possible due to a safety concern as judged by the investigator) then all assessments related to trial product discontinuation must be completed at visit 22A.

Subjects discontinuing after Visit 12 (Week 6)

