2.4 Secondary endpoints

2.4.1 Confirmatory secondary endpoints

If the effect of CSII treatment with fast-acting insulin aspart can be confirmed in the primary analysis, the trial also aims to confirm the superiority of CSII treatment with fast-acting insulin aspart, for a number of secondary confirmatory endpoints.

The steps used in the hierarchical testing procedure are as follows:

Step 1 (Primary analysis): HbA_{1c} non-inferiority of fast-acting insulin aspart versus NovoRapid[®]

Step 2: 1-hour PPG increment (meal test) superiority of fast-acting insulin aspart versus NovoRapid[®]

Step 3: HbA_{1c} superiority of fast-acting insulin aspart versus NovoRapid[®]

Step 4: 1,5-anhydroglucitol superiority of fast-acting insulin aspart versus NovoRapid[®]

Step 5: time spent in low IG (≤ 3.9 mmol/L [70 mg/dL]) superiority of fast-acting insulin aspart versus NovoRapid[®]

The primary estimand for the primary endpoint will be repeated for the confirmatory secondary endpoints, change from baseline in 1-hour PPG increment (meal test), change from baseline in 1,5-anhydroglucitol and change from baseline of time spent in low IG (≤ 3.9 mmol/L [70 mg/dL]) during CGM 16 weeks after randomisation. The analyses related to these estimands are defined below and will be used for the decisions to continue or not, throughout the hierarchical testing procedure. These analyses will be based on the FAS and use the in-trial observation period.

The secondary analysis 4) will also be repeated for the confirmatory secondary endpoints. The analysis will be based on the FAS and using the on-treatment observation period.

Change from baseline in 1-hour PPG increment 16 weeks after randomisation (meal test) (Step 2)

As the second step of the hierarchical testing procedure, change from baseline in 1-hour PPG increment 16 weeks after randomisation will be tested for superiority of fast-acting insulin aspart compared to Novo Rapid[®].

The 1-hour PPG increment will be analysed based on the laboratory measured values in the meal test, and is derived as the 1-hour PPG measurement minus the pre-prandial PG.

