2.4.2.2 Safety endpoints

All safety endpoints will be compared using the on-treatment observation period. In terms of adverse events, as a minimum, serious adverse events will be tabulated separately also using the in-trial observation period.

All events in the in-trial observation period will be listed with information about whether it appeared in the on-treatment observation period or not.

Number of treatment emergent Adverse Events (AEs)

AEs will be coded using the Medical Dictionary for Regulatory Activities (MedDRA). AEs will be presented based on system organ class and preferred terms.

A Treatment Emergent Adverse Event (TEAE) is defined as an event that has an onset date on or after the first day of exposure to randomised treatment, and no later than seven days after the last day of randomised treatment.

TEAEs are summarised descriptively, whereas AEs not defined as treatment emergent are presented in listings, including AEs reported in the 30-day follow-up period. The summaries of TEAEs are made displaying the number of Subjects with at least one event, the percentage of Subjects with at least one event, the number of events and the event rate per 100 patient years of exposure. These summaries are done by seriousness, severity, relation to insulin treatment, relation to technical complaint, premature treatment discontinuation due to AEs, AEs leading to withdrawal from trial and outcome.

Furthermore, summary tables based on system organ class and preferred terms are made for:

- All TEAEs
- Serious TEAEs
- Possibly or probably related TEAEs
- Severe TEAEs
- TEAEs with preferred term that are experienced by at least 5% of the Subjects in any treatment arm or by at least 5% of all Subjects

For AEs where additional information is recorded, this will be listed.

AEs occurring during the run-in period are considered non-treatment emergent and will be summarised separately.

Number of treatment emergent infusion site reactions

Infusion site reactions occurring during the trial will be summarised using the on-treatment observation periods, and listed.

Classification of Hypoglycaemia

Treatment emergent: hypoglycaemic episodes will be defined as treatment emergent if the onset of the episode occurs on or after the first day of IMP administration after randomisation and no later than one day after the last day on IMP.

Nocturnal hypoglycaemic episodes: are episodes occurring between 00:01 and 05.59 both inclusive.

[figure not shown]

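### The single 7-day on-treatment window lets some meal-test, CGM and SMPG values taken on marketed insulin into the secondary (de jure) analyses; the expected effect is small and the confirmatory tests are untouched

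*SAP*

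**What the plan says.** **The window.** SAP section 2 (General considerations) and Protocol section 17 define one on-treatment period for all endpoints, from first dose to seven days after the last: "The on-treatment observation period includes data collected up to and including 7 days after discontinuation of randomised treatment".

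**The target.** The secondary (de jure) estimand in SAP section 2 is the difference between treatments "if Subjects continue on-treatment until 16 weeks". Analysis 4 addresses it on the on-treatment period. SAP section 2.4.1 adds: "The secondary analysis 4) will also be repeated for the confirmatory secondary endpoints", which brings in the 1-hour PPG increment (Step 2) and time in low IG (Step 5). SAP section 2.4.2.1 repeats most supportive efficacy endpoints, SMPG included, on the same period.

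**Discontinuers.** Under Protocol section 8.1.8.1 the Visit 22A meal test is meant to be done on trial product, with an exception where the investigator judges this not feasible for safety reasons. The section also states: "Confirmation that the meal test was performed on trial product will be recorded in the eCRF". Subjects stopping after Visit 12 are switched to a marketed product at Visit 22A. Those stopping between Visits 20 and 22 nevertheless have their CGM and 7-7-9-point assessment at Visit 22 as planned. Later, the same section says that Visit 22A replaces Visit 22 when it falls more than 12 weeks after randomisation.

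**Data handling.** The SAP's general rule is that "all observed values from randomised subjects will be used in all statistical analyses". Where two values fall on the same visit, "for the secondary estimand the reallocated on-treatment value will be used". For hypoglycaemic episodes, SAP section 2.4.2.2 uses a shorter limit: "no later than one day after the last day on IMP".

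**The concern.** HbA1c is described in Protocol section 3.2 as a measure of long-term control, so a value drawn a few days after the last dose still mostly reflects trial product. A meal-test increment, a sensor trace or an SMPG profile reflects the insulin being infused at that time. Counting such a value as on-treatment after the switch does not match an estimand defined by staying on treatment. The SAP itself warns that the marketed product discontinuers move to may bring the arms together, and the de jure analysis is meant to be free of that.

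Nothing in the SAP prevents it. The eCRF confirmation for the meal test is collected, but no analysis rule refers to it. Time in low IG is computed from the first valid sensor value over the full profile duration, with no cut at the last dose. The one-day limit for hypoglycaemia shows that a shorter window for acute glucose events was thought appropriate elsewhere in the same plan.

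At stake is how faithfully the secondary analyses of Steps 2 and 5, and the on-treatment SMPG analyses, reflect their estimand.

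**Working it through.** **Inputs from the documents.** Step 2 difference 0.9 mmol/L, SD 3.4, two-sided 5%, 225 per arm; treatment discontinuation perhaps as low as 4%, half of it trial discontinuation (SAP section 2.1); CGM profiles of 11 to 13 days (Protocol section 8.5.1); Visit 20 at week 14 and Visit 22 at week 16 (Protocol section 2).

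**Assumptions, not in the documents.** The share f of faster aspart subjects whose on-treatment value was taken on marketed insulin; no residual treatment effect after the switch; no change in the comparator arm; SD unchanged. No effect size or SD is given for Step 5, so only relative dilution can be shown.

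**Plan's own figure.** Standard error = 3.4 × √(2/225) = 0.3206. Noncentrality = 0.9 / 0.3206 = 2.81. Power by the noncentral t distribution is 80.0%, matching SAP Table 2-2.

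**Step 2.** Expected discontinuers per arm: 0.04 × 225 = 9. Diluted effect = 0.9 × (1 − f).

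| Off-product share f | Effect (mmol/L) | Power |
|---|---|---|
| 0.5% | 0.896 | 79.6% |
| 1% | 0.891 | 79.2% |
| 2% | 0.882 | 78.4% |
| 4% (all 9) | 0.864 | 76.7% |

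The largest loss at the planned rate is 0.9 × 0.04 = 0.036 mmol/L, or 0.036 / 0.3206 = 0.11 standard errors. As a stress case, 10% discontinuation with every value off product gives 0.81 mmol/L and 71.3%.

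**Step 2 after the fix.** If the removed values are imputed from the subject's own arm, the target returns to 0.9. Approximate power, counting only observed subjects, is then:

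- 4% removed (216 per arm): 78.4%, against 76.7% with the window.
- 2% removed (220.5 per arm): 79.2%, against 78.4% with the window.

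These powers only indicate scale, because the de jure analysis is not a confirmatory test.

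**Step 5.** If discontinuations are uniform over 16 weeks, those between Visits 20 and 22 number 9 × 2/16 = 1.125 per arm. Counting their whole profile as off product gives 1.125 / 225 = 0.5%. If instead all 4% had 7 off-product days in the profile, dilution would be 0.04 × 7/13 = 2.2% to 0.04 × 7/11 = 2.5%.

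**Who can contribute.** Completers cannot: they switch only after the Visit 22 meal test (Protocol section 8.3.7). Subjects stopping at or before Visit 12 are asked to stay on product until Visit 22B, and their CGM is reallocated to Visit 14, not week 16.

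**The case against.** Several points against the concern are sound.

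- **Narrow Step 2 route.** It needs a discontinuer who used the safety exception and was tested within 7 days of the last dose. The 4% figure requires every expected discontinuer, including the half who leave the trial, to be such a case. It is a ceiling, not a forecast.
- **Uncertain Step 5 route.** If Visit 22A replaces Visit 22 for late stoppers, the post-switch CGM may not take place at all.
- **Review before lock.** SAP section 2.2 provides for a blinded review that documents excluded observations. The on-product confirmation could be considered there, but the SAP does not say that it will be.

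Three stronger readings are tempting, and the documents do not support them.

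- A reader might infer that the reallocation rule itself admits off-product data. It applies only when two values compete for one visit, and it then prefers the Visit 22A value, normally on product, over a later post-switch one. It usually reduces dilution. The gap is in how the window defines on-treatment.
- A reader might infer that the bias always runs towards no difference. The switch is to a marketed product of the investigator's choice, not necessarily NovoRapid; comparator-arm values can move too; and subjects tested under a safety exception are not a random sample.
- A reader might infer that the confirmatory results for Steps 2 and 5 are compromised. They use the in-trial period, and SAP section 3 confirms that type I error is controlled only for the primary estimand.

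The mismatch between window and estimand remains: the safety exception is written into the protocol, and the SAP never uses the confirmation that would identify those tests.

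**Conclusion.** The point holds as a minor misalignment in secondary analyses. One window serves endpoints with very different time scales, so a few meal-test, CGM and SMPG values taken on marketed insulin can be counted towards an effect defined by subjects who "continue on-treatment until 16 weeks".

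The Step 2 loss is at most 0.036 mmol/L of 0.9 at the planned discontinuation rate, and realistically less. The Step 5 dilution is about 0.5% under uniform discontinuation, and that route exists only if late stoppers do continue CGM to Visit 22. Both figures assume that the treatment effect vanishes at the switch and that only the faster aspart arm is affected. The direction is therefore probable rather than certain. Discontinuation above 4% would increase the size in proportion.

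The confirmatory hierarchy, its decisions and its error control are unaffected. The change is worth making because it is cheap and aligns the analysis with its stated target.

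**What to change.** In SAP section 2:

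1. Keep the 7-day window for HbA1c and 1,5-anhydroglucitol, treated here as the slower markers.
2. For de jure analyses of meal-test endpoints, use a discontinuer's test only if the eCRF confirms it was done on trial product. Completers' Visit 22 tests precede the switch and stay in.
3. For CGM and SMPG, cut the data at the last dose, or at one day after it to match the hypoglycaemia rule. State which. For time in low IG, apply the cut to both the accumulated time and the profile duration.
4. Treat excluded values as missing and impute them from the subject's own randomised arm. Say explicitly that the Step 2 model in SAP section 2.4.1, which imputes both arms from NovoRapid data, is not used here, because it would bring the dilution back.

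Separately, the two statements in Protocol section 8.1.8.1 on late stoppers (CGM at Visit 22 as planned, and Visit 22A in place of Visit 22) must be reconciled, since they determine whether the Step 5 route exists.

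The cost is SAP wording, a filter on data already collected, and a few more imputed values in a secondary analysis.
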